## 9.14.3 Exploratory Efficacy Analyses

The following exploratory analyses will be performed on the FAS for each central reader.

## 9.14.3.1 Composite Cu-SAR-bisPSMA PET/CT Day 0 and Day 1 Results

CDR, participant- and region-level PPV, and DR, as described in the primary and secondary analyses, will be analyzed separately with the proportions derived using the best outcome from both Day 0 and Day 1.

For the composite CDR and PPV a participant or region (if applicable) will be classed as TP if they meet one of the following criteria:

- Classed as TP on Day 0 (regardless of classification on Day 1)
- Classed as TP on Day 1 (regardless of classification on Day 0)

September 4, 2024 CONFIDENTIAL Page 31 of 46

For the composite PPV a participant or region will be classed as FP for the denominator if they meet one of the following criteria and are not classed at TP based on the composite PPV TP criteria above:

- Classed as FP on Day 0 and Day 1
- Classed as FP on Day 0 and classed as either TN, test-negative or non-evaluable on Day 1
- Classed as FP on Day 1 and classed as either TN, test-negative or non-evaluable Day 0

For DR a participant will be classed as having a positive composite Cu-SAR-bisPSMA PET/CT scan if they meet one of the following criteria:

- A positive Cu-SAR-bisPSMA result on both Day 0 and Day 1.
- A positive Cu-SAR-bisPSMA result on Day 0 and negative, missing, or equivocal Cu-SAR-bisPSMA result on Day 1.
- A negative, missing, or equivocal Cu-SAR-bisPSMA result on Day 0 and a positive Cu-SAR-bisPSMA result on Day 1.

The total number of scanned participants (i.e., the denominator for DR) will be the number of participants who underwent a Cu-SAR-bisPSMA PET/CT scan on both Day 0 and Day 1.

The composite CDR, participant- and region-level PPV, and DR will be summarized with 95% Exact Clopper-Pearson CIs for each central reader.

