2.7.3 Exploratory Objectives and Endpoints

The exploratory study objectives and endpoints to be evaluated in this study are presented in Table 3.

Table 3 Exploratory Study Objectives and Endpoints

Objective	Endpoint
To evaluate the reproducibility of the ⁶⁴ Cu-SAR-bisPSMA PET/CT readings and consistency among readers.	Intra-reader variability per reader.Inter-reader variability expressed by kappa statistics.
To assess the impact of ⁶⁴ Cu-SAR- bisPSMA PET/CT on disease management.	Proportion of participants with any change in intended PC treatment due to either the Day 0 or Day 1 scan.

Composite performance of the Day 0 and Day 1 ⁶⁴ Cu-SAR-bisPSMA PET/CT scans.	 Composite CDR defined as the proportion of TP participants on the Day 0 and/or Day 1 scan out of all participants with a Day 0 and/or Day 1 scan. Composite participant/region-level PPV defined as the
	proportion of TP participants/regions on the Day 0 and/or Day 1 scan out of all participants/regions with a positive Day 0 and/or Day 1 scan.
	• Composite DR defined as the proportion of participants with a positive Day 0 and/or Day 1 scan out of all participants with a Day 0 and/or Day 1 scan.
To determine the effect of baseline variables on the CDR, PPV and DR of ⁶⁴ Cu-SAR-bisPSMA PET/CT.	CDR, participant- and region-level PPV and DR of the Day 0 and/or Day 1 scan as a function of baseline variables.
To explore the correlation between ⁶⁴ Cu-SAR-bisPSMA PET-positivity and Reference Standard results.	Relationship between PET-positivity (biodistribution measures such as SUVs and lesion-to-background ratio), versus true/false positivity and as a function of lesion location and size.
To assess the lesion-level performance of ⁶⁴ Cu-SAR-bisPSMA PET/CT.	• Difference in the number of lesions detected per participant on the Day 0 versus the Day 1 scan.
	• Overall agreement rate on the Day 0 and Day 1 scans, defined as the number lesions with matching subregion divided by the total number of lesions identified across all scans by either imaging.
	• Overall agreement rate on the Day 0 and reference scans, defined as the number lesions with matching subregion divided by the total number of lesions identified across all scans by either imaging.
	• Overall agreement rate on the Day 1 and reference scans, defined as the number lesions with matching subregion divided by the total number of lesions identified across all scans by either imaging.

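### In SAP 9.14.3.1 the composite false-positive list omits a missing other-day scan, so composite PPV can be biased upward if read literally, and the composite DR numerator and denominator do not match

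*SAP*

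**What the plan says.** Protocol section 2.7.3 (Table 3) defines composite PPV as TP participants or regions "out of all participants/regions with a positive Day 0 and/or Day 1 scan". Composite CDR and DR are likewise based on participants scanned on either day.

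SAP section 9.14.3.1 implements this with lists.

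- **Composite TP:** "Classed as TP on Day 0 (regardless of classification on Day 1"), and the mirror rule for Day 1.
- **Composite FP, provided the case is not a composite TP:** "Classed as FP on Day 0 and Day 1"; or "Classed as FP on Day 0 and classed as either TN, test-negative or non-evaluable on Day 1"; or "Classed as FP on Day 1 and classed as either TN, test-negative or non-evaluable Day 0".
- **Composite DR, numerator:** positive on both days; or a positive "result on Day 0 and negative, missing, or equivocal" result on Day 1; or the mirror case, which begins "A negative, missing, or equivocal".
- **Composite DR, denominator:** "The total number of scanned participants (i.e., the denominator for DR) will be the number of participants who underwent a" PET/CT scan on each of the two days.

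The table of deviations in SAP section 8.0 declares no change to these endpoints.

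**The concern.** The TP rule is open and the FP rule is closed. The FP list leaves out a scan not done, although the DR list a few lines below names that state. Take two men, each PET-positive on Day 0 with no Day 1 scan. One has a positive Reference Standard and counts as TP. The other has a negative one and, on the literal text, is neither TP nor FP. Entry to the PPV denominator would then depend on the outcome being estimated.

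The DR list has the opposite gap: it names missing but not non-evaluable. Its numerator also admits men whom its denominator excludes.

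At stake is whether two programmers working from this SAP would produce the same composite PPV and DR, and whether either result would match the protocol.

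**Working it through.** **Planning inputs (Protocol 10.3, SAP 4.2).** 40 evaluable men, CDR 42%, 65% PET-positive, 1.3 positive regions per positive man, region-level PPV 65%. The plan's own figures reproduce:

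- Regions: 40 × 0.65 × 1.3 = 33.8, about 34. Enrolment: 40/(1 − 0.20) = 50.
- CDR: 14/40 is the smallest count whose exact 95% lower bound exceeds 20% (20.6%). Power at 42% is 85.5%, against the stated more than 85%.
- PPV: 20/34 is the smallest count whose lower bound exceeds 40% (40.7%). Power at 65% is 82.6%, against the stated more than 80%.

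The documents give no planning figure for composite PPV and no missing-scan rate.

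**Which records are lost.** Allow six states per day: TP, FP, TN, test-negative, non-evaluable, scan missing. Of the 36 Day 0/Day 1 pairs, nine contain an FP and no TP. Seven of these meet a composite FP rule. The two that do not are FP/missing and missing/FP. The corresponding TP/missing and missing/TP pairs both count as TP.

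**Size for PPV.** Let m be the share of composite FPs with no other-day scan. The protocol definition gives TP/(TP + FP); the literal SAP rule gives TP/(TP + FP(1 − m)). Single-day planning rates stand in for the composite, which is an assumption.

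- Participants: positive = 40 × 0.65 = 26; TP = 40 × 0.42 = 16.8; FP = 26 − 16.8 = 9.2; PPV = 16.8/26 = 64.6%.
- Regions: TP = 34 × 0.65 = 22.1; FP = 34 − 22.1 = 11.9; PPV = 65.0%.

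| m (assumed) | Participant PPV | Region PPV | Excess, points |
|---|---|---|---|
| 0% | 64.6% | 65.0% | 0 |
| 2% | 65.1% | 65.5% | 0.5 |
| 5% | 65.8% | 66.2% | 1.2 |
| 10% | 67.0% | 67.4% | 2.4 |
| 20% | 69.5% | 69.9% | 4.9 |

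In whole counts, dropping one FP moves participant PPV from 17/26 = 65.4% (95% CI 44.3 to 82.8) to 17/25 = 68.0% (46.5 to 85.1), and region PPV from 22/34 = 64.7% to 22/33 = 66.7%. That is 2.6 and 2.0 points.

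**Size for DR.** Take 50 men and round 50 × 0.65 = 32.5 to 33 positive, so 33/50 = 66.0%.

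- One of the 33 is positive on Day 0 and non-evaluable on Day 1, with both scans done. He stays in the denominator but meets no positive criterion: 32/50 = 64.0%, a loss of 2 points.
- One of the 33 is positive on Day 0 with no Day 1 scan. The protocol gives 33/50 = 66.0%. The SAP numerator is 33 and its denominator 49: 67.3%. With numerator and denominator restricted to the same men it is 32/49 = 65.3%. In the SAP version the numerator is not a subset of the denominator, so an exact binomial interval does not strictly apply.

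**The case against.** The strongest reply is that the PPV and DR lists work on different variables. The PPV list uses per-timepoint classes, and SAP section 7.8 defines only TP, TN, FP and non-evaluable, plus test-negative for summaries. None of these is a missing class, and the composite TP and FP rules together cover all of them. If a scan not done is placed in the nearest class, non-evaluable, the second and third FP rules catch it and nothing is lost. Section 7.8 also refers to a programming supplement, not among the documents, that may settle this.

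This has force. A reader might infer that composite PPV *is* biased upward; the documents do not establish that. Nor do they support the inference that missing scans can only raise it. The one-way direction holds only for the literal rule against the protocol definition on the same data. A missing scan can also lower composite PPV, for instance when a man who is FP on Day 0 would have been TP on the Day 1 scan that was not done. The 20% allowance in the sample size is for non-evaluable participants, including loss to follow-up, and is not a missing-scan rate. Both scans follow one dose about a day apart, so missed scans may be few.

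The reply does not remove the gap. SAP 7.3 leaves missing values as missing unless otherwise indicated, and converts missing to non-evaluable only for Reference Standard adjudications. Section 7.8 ties non-evaluable to a PET/CT result or to the Reference Standard, and 7.7 to a subregion marked as such; neither mentions a scan not done. Section 9.14.1 excludes men without a scan under a rule separate from the one for a non-evaluable Reference Standard. The Full Analysis Set does not require both scans. The mismatch between the DR numerator and denominator does not depend on how a missing scan is coded.

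**Conclusion.** The point holds as a gap in specification that can produce an outcome-dependent denominator. On the literal text, composite PPV can exceed the protocol's definition by about 2 to 3 points per dropped FP at the planned size. It is exactly right if no scan is missing or if a missing scan is coded non-evaluable. The percentages by m rest on assumed missing-scan rates and on single-day planning values. The composite DR rule is internally inconsistent and departs from the protocol without a declared deviation; one affected man moves it by about 1 to 2 points in the examples shown.

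The consequence is small. These endpoints are exploratory, no formal hypothesis is tested, and the co-primary CDR and PPV are calculated separately by day.

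**What to change.** In SAP section 9.14.3.1:

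- Define composite FP as FP on at least one day and TP on neither.
- Define composite PET-positive as positive on at least one day, regardless of the other.
- Set the composite DR denominator to participants with a Day 0 scan, a Day 1 scan or both. If the two-scan denominator is preferred, restrict the numerator to the same men and declare the deviation in section 8.0.
- State how a scan not done is coded, and make the programming supplement agree.

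This takes a few sentences and no new data. Composite PPV may come out slightly less favourable. The co-primary endpoints and the sample size do not change.

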#### 9.14.3.2 Function of Baseline and Other Variables of Interest

CDR, participant- and region-level PPV, and DR of both the Day 0 and Day 1 scans will be summarized by the following variables:

- PSA at baseline:  $<0.5, 0.5 <1.0, 1.0 <2.0, 2.0 <5.0, \ge 5.0 \text{ ng/mL}.$
- PSA doubling time at baseline (PSADT):  $<3.0, 3.0-8.9, 9.0-14.9, \ge 15.0$  months.
- PSA velocity at baseline: 0 to <0.05, 0.05 to <0.10, 0.10 to <0.20, \ge 0.20 ng/mL/y.
- Testosterone at baseline: <230, 230-350, >350 ng/dl.
- Standardized uptake value (SUV) max:  $\leq 2, 2 < 5, 5 < 10, \geq 10$ .
- Initial treatment received (2 categories): radical prostatectomy OR radiation therapy, cryotherapy and brachytherapy.
- Reference Standard Level of Evidence Used: Level 1, Level 2, Level 3
  - Level 1 = histopathology (regardless of imaging results or PSA response being available).
  - Level 2 = imaging results (regardless of PSA response being available) but no contributing histopathology information,

September 4, 2024 CONFIDENTIAL Page 32 of 46

- Level 3 = PSA response only ((i.e., no contribution of histopathology or imaging result information (participant-level only)).
- Size of largest lesion (long axis) identified on  $^{64}$ Cu-SAR-bisPSMA PET/CT central reader scan:  $0 <0.5, 0.5 <1.0, \ge 1.0$  cm.
- Time to Cu-SAR-bisPSMA PET/CT scan from dosing (Day 0 only): 1 − 2 hours, 2 -4 hours.

CDR, participant and region-level PPV, and DR will be summarized for each level of the baseline categorical variables with CDR, PPV, and DR values in each category by central reader. Region-level parameters will only be summarized for the "All regions" category and not the individual regions.

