7.5 Diagnostic Efficacy Assessments

7.5.1 Assessment of the Composite Reference Standard

The composite Reference Standard may consist of histopathology, conventional imaging modalities that are routinely used in the diagnosis and staging of PC and PSA levels. ⁶⁴Cu-SAR-bisPSMA scans will not form part of the Reference Standard.

The Reference Standard status will be determined by an independent, blinded, central expert panel. The expert panel will establish the Reference Standard disease status (on a participant-and region-level) for each participant individually, using information provided by the site's Investigator. The experts will be blinded as described in Section 4.3.

The Investigator will be required to submit all relevant clinical evidence available for the participant to enable the assessment of the Reference Standard. Relevant evidence will include:

- All available histopathology reports related to the participants disease history;
- All available conventional scans and related local reports collected as part of Screening (within 60 days of Day 0) and Follow-up (within 180 days [±15 days] of Day 0);
- PSA levels recorded as part of Screening and Follow-up;
- All available PC related symptom and treatment history;

The composite Reference Standard will be hierarchical in nature, with three levels of evidence that will be applied as follows:

- Level 1: Evaluable histopathology from biopsy or surgery OR in case that histopathology is not available, inconclusive or negative:
- Level 2: Conventional imaging procedures OR if neither histopathology or conventional imaging are available or informative:
- Level 3: Confirmed PSA response following radiation or other salvage focal therapy (as long as no concomitant ADT is given), defined as total PSA decline by ≥50% from baseline, confirmed by a second value within four weeks as per the Prostate Cancer Working Group 3 criteria²⁵.

The expert panel will use the collective information to determine and record each region with histopathology demonstrating PC, the number of lesions suspicious for PC detected on conventional imaging in each anatomical subregion and whether the participant achieved confirmed PSA response (if applicable).

Region(s) with no histopathology demonstrating PC or no unequivocal lesion recorded in any of the anatomical subregions on conventional imaging will be deemed negative for the region level Reference Standard status.

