## • Non-evaluable:

o A region that has either non-evaluable (NE) Cu-SAR-bisPSMA PET/CT results for a specific timepoint (Day 0 or Day 1) or has a non-evaluable or inconclusive Reference Standard will not be assigned for that timepoint.

Assessments of **Participant-Level** Reference Standard against the Cu-SAR-bisPSMA PET/CT results:

• True Positive:

September 4, 2024 CONFIDENTIAL Page 22 of 46

- A participant with at least one TP region and/or at least one unequivocal Cu-SAR-bisPSMA positive lesion in any region and a confirmed PSA response to radiation or other salvage focal therapy.
  - Confirmed PSA response following radiation or other salvage focal therapy (as long as no concomitant ADT is given) = total PSA decline ≥50% from baseline, confirmed by a 2nd value within 4 weeks per Prostate Cancer Working Group 3 criteria.

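### The exploratory table of PPV by level of reference evidence partly sorts cases by their reference result, and on no reading gives PPV against histopathology

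*SAP*

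**What the plan says.** SAP 9.14.3.2 breaks CDR, participant- and region-level PPV, and detection rate (DR) down by the level of reference evidence used. The strata are:

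- Level 1: "Level 1 = histopathology (regardless of imaging results or PSA response being available").
- Level 2: "Level 2 = imaging results (regardless of PSA response being available) but no contributing histopathology information".
- Level 3: "Level 3 = PSA response only", which the SAP restricts to the participant level.

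The hierarchy itself is in Protocol 7.5.1. A case moves from histopathology to imaging "in case that histopathology is not available, inconclusive or negative". The third level reads "Level 3: Confirmed PSA response following radiation or other salvage focal therapy"; no negative counterpart is defined there.

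SAP 7.8 sets true-positive (TP) status. A PET-positive region with positive histopathology is TP. So is a region in which a PET-positive subregion matches an unequivocal lesion on conventional imaging. At participant level, TP also covers anyone with an unequivocal PET "positive lesion in any region and a confirmed PSA response to radiation or other salvage focal therapy".

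Three things are not stated: whether a negative biopsy counts as contributing, whether the level is attached to a region or a participant, and how the level is programmed. SAP 7.8 leaves programming detail to a supplement that is not part of these documents.

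**The concern.** A table of PPV by evidence level invites one reading: how well PET findings hold up where the reference is strongest. That works only if a case's stratum does not depend on whether the reference confirmed PET. Here it partly does. Under the protocol, histopathology settles a case at Level 1 only when positive. Level 3 is entered through a PSA response. Confirmed cases are drawn into Levels 1 and 3, and refuted ones are left in Level 2. A Level 1 PPV of 100% could then be taken as histological confirmation of every PET finding when it only restates the sorting rule. Biopsies that failed to confirm PET would not be visible in that table.

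**Working it through.** **Planning totals (Protocol 10.3, SAP 4.2).** 40 × 0.65 = 26 PET-positive participants; 26 × 1.3 = 33.8, about 34 positive regions. The stated power reproduces: CDR passes at 14/40 or more, power 85.5% (stated above 85%); PPV passes at 20/34 or more, power 82.6% (stated above 80%); 40/(1 − 0.20) = 50. At the assumed 65% PPV, 34 regions give about 22 TP and 12 false positives (FP). The documents give no figure for the by-level table.

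**Region PPV = TP/(TP + FP), level attached to the region.** Biopsy counts are assumed, and every negative biopsy is taken to be imaging-negative too. Let x be histology-positive and b histology-negative regions.

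- Protocol routing: Level 1 = x/x; Level 2 = (22 − x)/(34 − x).
- Negative biopsies kept in Level 1: Level 1 = x/(x + b); Level 2 = (22 − x)/(34 − x − b).

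| x | b | Routed: Level 1 | Routed: Level 2 | Kept: Level 1 | Kept: Level 2 |
|---|---|---|---|---|---|
| 4 | 2 | 4/4 | 18/30 = 60% | 4/6 = 67% | 18/28 = 64% |
| 4 | 6 | 4/4 | 18/30 = 60% | 4/10 = 40% | 18/24 = 75% |
| 8 | 2 | 8/8 | 14/26 = 54% | 8/10 = 80% | 14/24 = 58% |
| 8 | 4 | 8/8 | 14/26 = 54% | 8/12 = 67% | 14/22 = 64% |
| 8 | 6 | 8/8 | 14/26 = 54% | 8/14 = 57% | 14/20 = 70% |
| 12 | 2 | 12/12 | 10/22 = 45% | 12/14 = 86% | 10/20 = 50% |
| 12 | 6 | 12/12 | 10/22 = 45% | 12/18 = 67% | 10/16 = 62.5% |

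Routed, Level 1 is 100% whatever b is, and all 12 FPs sit in Level 2. Exact 95% CIs: 8/8, 63% to 100%; 8/12, 35% to 90%.

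**Keeping negative biopsies in Level 1 still does not give PPV against histopathology.** Take x = 8 and b = 4, with 2 of the 4 negatives imaging-positive in a matching subregion. Those 2 are TP under SAP 7.8. Level 1 becomes (8 + 2)/12 = 83%, while histology-only PPV is 8/12 = 67%. The two agree only if all four negatives are also imaging-negative.

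**Level attached to the participant.** Assume the reader marks the histology-positive region, and let other positive regions have PPV s. With 1.3 regions per positive participant, Level 1 region PPV = (1 + 0.3s)/1.3: 77% at s = 0, 92% at s = 0.65, 100% at s = 1. It is raised, not fixed.

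**Participant PPV.**

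- Level 3: every member is a PSA responder, so every PET-positive member is TP and PPV is 100%.
- Level 1: biopsies follow the local read (Protocol 7.4), but TP status uses each central reader. If a PET-positive reader marks the histology-positive region with probability q, and otherwise an imaging TP arises elsewhere with probability t, PPV = q + (1 − q)t. For assumed q of 0.7 to 1 and t = 0, that is 70% to 100%.

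**CDR.** Its denominator includes PET-negative participants. In Level 3 it equals the DR of that stratum; in Level 1 it is at most the DR. Illustration: 40 participants, 26 PET-positive, 17 TP (0.42 × 40 = 16.8), 9 FP. Assume 6 TPs in Level 1, 2 in Level 3, and no PET-negatives in either. Level 2 then has PPV 9/18 = 50% and CDR 9/32 = 28%, against 17/26 = 65% and 17/40 = 42.5% overall.

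**The case against.** The strongest reply is that the SAP line contains no positive-only condition. Read literally, an evaluable negative biopsy stays in Level 1, and a negative result can reasonably be said to contribute. Protocol 7.5.1 itself opens Level 1 with evaluable histopathology, and the programming supplement may settle the matter. This stands: 100% in Level 1 follows from one reading only. It does not rescue the table, because the literal reading departs from the protocol's routing and still credits biopsy-negative, imaging-positive regions as Level 1 successes.

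A reader might infer that Levels 1 and 3 must both show CDR and PPV near 100%. The documents do not support that. Level 3 has no region-level PPV, CDR is not forced to 100%, and Level 1 PPV is fixed only at region level, with protocol routing and a per-region label. Nor is a negative Level 3 result expressly excluded. SAP 7.7 lists PSA response among the reference datapoints and allows negative results, and SAP 7.8 asks only for an evaluable reference before assigning a participant-level FP. The 100% for Level 3 rests on the stratum as SAP 9.14.3.2 defines it, by response.

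A reader might also infer that biopsies refuting PET will go unreported. They will not: SAP 9.10 summarises histopathology by region, and SAP 9.13 summarises the evidence level with its imaging, histopathology and PSA detail. What is missing is a PPV tied to those results.

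Finally, sending negative biopsies on to imaging is defensible for the primary analysis, since a biopsy can miss a lesion. That is a reason to leave the hierarchy alone, not to stratify PPV by it.

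**Conclusion.** The point holds in limited form. The strata depend partly on the reference result, so differences in PPV between levels partly reflect sorting. How far depends on choices the SAP leaves open. Level 3 participant PPV is 100% under the stated definition. Level 1 region PPV is 100% under protocol routing with a per-region label, and otherwise raised or variable. No reading yields PPV against histopathology. In the illustration the gap is 8/8 against 8/12; across the assumed counts with at least two negative biopsies, all imaging-negative, the relabelled Level 1 figure runs from 40% to 86%. All biopsy counts are assumptions; only the totals of 34 regions and 65% PPV come from the plan.

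Severity is minor. The summary is exploratory, SAP 4.1 plans no formal testing, and the primary CDR and PPV do not depend on this label.

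**What to change.** Amend SAP 9.14.3.2 and leave the primary hierarchy unchanged:

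1. Define the level by the best evaluable evidence obtained, whatever its result and whatever the PET call. State the unit: region for region-level PPV, participant for participant-level PPV. Making the label independent of the PET call avoids fixing DR within a stratum.
2. Add a separate histology-only PPV: histology-positive / (histology-positive + histology-negative), among PET-positive regions with evaluable follow-up histopathology, per central reader, with an exact CI. Keep it distinct from the composite PPV in Level 1.
3. For Level 3, show PSA responders and non-responders among participants given focal therapy with PSA follow-up and no informative histopathology or imaging, or give counts without PPV. Say what counts as informative: Protocol 7.3.3 requires follow-up imaging for everyone, so excluding all evaluable imaging could nearly empty the stratum.
4. State that CDR and DR by level are not to be read as measures of accuracy.

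The cost is SAP wording and one table. Histopathology results, on-study treatment and PSA after focal therapy are already collected. The drawbacks are small cells with wide intervals and a Level 1 figure that will probably be lower.
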